6.7 Identification of relevant lesions

On a weekly basis, 2 study attendings will independently review the results of the EGDs/MCCs that were performed during the week and complete a report sheet. A per-patient analysis of any abnormal lesion/s will be performed. During this analysis, the physicians will be asked if either the MCC or MCC-T or the EGD identified a lesion that would be of high likelihood to explain the patient's symptoms. If a responsible lesion is identified, then the physicians will review both the MCC and EGD to see if the lesion(s) were identified on both exams. Findings will be graded on a three-tier scale as follows:

- **D0:** finding is unlikely to be related to patient's presenting complaint
- **D1:** finding is of a medium likelihood to be related to the patient's presenting complaint
- **D2:** finding is of a high likelihood to be related to the patient's presenting complaint.

In addition, reviewing group will be responsible to perform a per-lesion analysis to assess whether all findings identified on the MCC and/or EGD were seen on the other exam (regardless of whether the finding is relevant to the patient's complaint). The statistician will then compare the results and obtain a Kappa statistic of the three sets of observations. And perform a statistical analysis as outlined under the analysis section.

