6.5 Visit 2 – MCC, MCC-T and EGD Procedure

Upon being checked in, the subject will be brought to the study area with the NaviCam System. A study staff member (NP/Attending/Fellow) trained in the MCC-T procedure will review the study procedure with the patient and confirm that the patient has been NPO for at least 8 hours. The patient will drink about 250ml of water prior to ingesting the capsule containing 1-2 drops of simethicone (infant formulation).

Examination of Esophagus:

The sensor array jacket will be attached to the patient. After the capsule is activated the patient will swallow the capsule (attached to a tether) in the sitting position. It will then be slowly lowered down the esophagus for a complete exam. Alternatively, the patient will be placed in the prone position with a 10° elevation of the head and ingest the capsule without the tether using sips of water. The study staff member will then record the video of the examination of the esophagus by moving the capsule down the esophagus using the magnetic field.

Images to be obtained:

1. Upper esophagus

2. Middle esophagus
3. Lower esophagus
4. Z line.
5. Any pathological lesions

Examination of Stomach:

Once the examination of the esophagus is complete and the capsule is in the stomach, the tether, if used, will be used to view the stomach as the patient drinks about 500 to 1000 cc of water with 4 drop of simethicone to ensure adequate gastric distention. The tether is then detached from the capsule by injecting air through the tether causing separation of the two components. The tether is withdrawn. Then instructed to lay down per physician instructions. The study staff member will begin controlling the device using the magnetic system. The patient will move their position in a predetermined patent to enhance complete visualization of the stomach as was done in the esophagus, a video will be recorded of the full examination. Photo documentation in accordance with a gastric mapping protocol will also be done. This includes images of the following:

- Distal Antrum
- Centered view of the pylorus
- Proximal Antrum
- Two pictures along the length of the incisura
- Distal body
- Mid/proximal body (lesser curvature)
- Mid/Proximal body (greater curvature)
- Gastric fundus
- Gastric cardia
- Any gastric pathology (e.g. gastric varices, gastric ulcers, gastropathy, polyps, etc.)

Examination of duodenum:

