Once the final images have been obtained the capsule will be piloted through the pylorus and into the duodenum. Following a brief examination (with photo documentation) of the duodenal bulb the capsule will be released into the small intestine with the video still running. Once the capsule reaches the distal duodenum the video recording can then stop, and the examination is completed.

Recording of MCC procedure:

The responsible study staff member will generate a procedure report documenting his/her findings that will then be cosigned by the study staff attending. This document will be deidentified and only linked to the patient by their study ID number. The document will be placed in the patient's study file along with the video recording of the entire procedure. The patient must be blinded to the findings at this time.

EGD Procedure:

At least two hours after the MCC-T ingestion the subject will be brought to the endoscopy procedure area; study staff will confirm that the patient has been NPO for at least 2 hours after the ingestion of water for the MCC or MCC-T procedure. If practicable, both procedures may be performed on the same day. If not, the EGD will be performed within 7 days and the patient will need to fast overnight prior to the EGD appointment and have nothing by mouth for at least 2 hours prior to arrival (per standard EGD instructions).

The patient will then be sedated using conscious sedation with midazolam and fentanyl or monitored anesthesia with propofol. The upper endoscopy will be performed in the left lateral position. The same photos of the esophagus, stomach, and duodenum will be obtained as described above. The doctor performing the upper endoscopy will not have any knowledge of the findings of the MCC procedure. The patient is then allowed to recover for 30 minutes in the recovery room and discharged.

Image management

Images from the MCC-T procedure will be stored in the Navicam system.

Images of the endoscopic procedure will be stored in Provation and EPIC as per routine.

Images from the MCC, MCC-T and EGD will be printed on photographic paper for comparison by the study team.

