10 DATA MANAGEMENT AND STATISTICAL CONSIDERATIONS

Study will be performed according to the protocol. The investigator will appoint a person that will be responsible to complete the Case Report Forms using the REDCap system, a secure data collection system. Source documentation will be either paper documents or the electronic medical record.

All relevant documents such as MCC images/videos, EGD images/videos, etc. will be uploaded to the EDC. Patient identification will be redacted from all data. Patients will be identified by their patient ID. The list of patient IDs will be kept in the site and will not be available for the sponsor.

The EDC system will provide streamlined communication between the study monitors, data managers and study coordinators. The system will allow the generation of queries which will need to be responded to and resolved by the relevant personnel.

De-identified color images will be used by the reader panel to compare MCC-T and endoscopy images.

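### Section 6.7 lets an attending grade an exam that he or she performed or cosigned, which can bias the D1/D2 grade of findings seen on only one exam

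*Combined protocol and SAP*

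**What the plan says.** **Grading.** Section 6.7 sets a weekly review in which "2 study attendings will independently review the results of the EGDs/MCCs that were performed during the week". They look at both exams openly, grade findings D0, D1 or D2 by how likely the finding is to explain the complaint, and check whether a responsible lesion was seen on both exams.

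**Use of the grade.** The synopsis, 4.2 and 10.5 count a D2 finding as positive and make the expert group's decision the gold standard. Section 10.1 instead names EGD as the gold standard.

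**Performing and signing.** Section 6.5 opens the capsule visit with this staffing: "A study staff member (NP/Attending/Fellow) trained in the MCC-T procedure will review the study procedure with the patient". The study staff member then moves the capsule and records the exam. The operator writes a "procedure report documenting his/her findings that will then be cosigned by the study staff attending".

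**Blinding and masking.** On the EGD, 6.5 says: "The doctor performing the upper endoscopy will not have any knowledge of the findings of the MCC procedure". On the images it says: "Images from the MCC, MCC-T and EGD will be printed on photographic paper for comparison by the study team". Section 10 adds: "De-identified color images will be used by the reader panel to compare MCC-T and endoscopy images". The redaction that section 10 describes is of patient identification.

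**Setting.** Section 5.1 describes a single centre. Section 10.6 plans 70 patients as a pilot, with no power calculation.

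**The concern.** The same grade of staff, at one site and within the same week, may operate the capsule, sign its report and then assign the grade on which the primary endpoint turns. D2 is a subjective call about likelihood. For a lesion seen on one exam only, the choice between D1 and D2 decides whether the other exam's failure to see it counts as a miss. A grader with a stake in one of the two exams could, without intending it, lean one way on exactly those findings. McNemar's test depends on the discordant patients alone, and with 70 patients there may be few of them.

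**Working it through.** The plan gives no figure on this point, so there is none to reproduce. The check is a reading of roles and safeguards, followed by an illustration with assumed counts.

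**1. Does any provision separate the roles?**

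- *Independent review (6.7).* The natural reading is independent of the other attending. It does not say independent of the exams.
- *Blinding of the endoscopist (6.5).* It applies when the EGD is done. It says nothing about who later grades.
- *De-identification (10).* It removes the patient's identity. It does not mask the operator or the report, and someone who did the exam that week may recognise it.
- *Comparison of images (6.5).* This is assigned to the study team, with no condition on prior involvement.
- *Identity of the endoscopist.* The plan does not say whether this doctor may be one of the graders.

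Nothing excludes overlap, and nothing says that it will occur.

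**2. Illustration.** Inputs: 70 patients (10.6). Assumed: 30% have a D2 finding, so 0.30 × 70 = 21, and the capsule misses 4 of them. Also assumed: the regrade sets the reference. The plan has no rule for disagreement between graders, so this last step cannot be taken from the text.

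Capsule sensitivity = detected / (detected + misses graded D2).

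- No regrading: 17/21 = 81%
- One miss moved from D2 to D1: 17/20 = 85%
- Two misses moved: 17/19 = 89%
- Opposite stake, one EGD-only finding moved from D1 to D2: 17/22 = 77%
- Opposite stake, two moved: 17/23 = 74%

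The exact 95% interval for 17/21 is 58% to 95%, so all of these lie inside it.

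**3. Range over other assumed counts.** Each row assumes equal numbers of D2 patients found by EGD only and by capsule only. The last two columns regrade one, then two, EGD-only findings.

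| Found by both / by one only, each side | Capsule sensitivity | D2 to D1 | D1 to D2 |
|---|---|---|---|
| 10 / 3 | 13/16 = 81.3% | 13/15 = 86.7%, 13/14 = 92.9% | 13/17 = 76.5%, 13/18 = 72.2% |
| 20 / 5 | 25/30 = 83.3% | 25/29 = 86.2%, 25/28 = 89.3% | 25/31 = 80.6%, 25/32 = 78.1% |
| 20 / 8 | 28/36 = 77.8% | 28/35 = 80.0%, 28/34 = 82.4% | 28/37 = 75.7%, 28/38 = 73.7% |

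One or two regrades move the estimate by about 2 to 12 percentage points.

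**4. Effect on McNemar's test.** Exact two-sided p = 2 × P(X ≥ max(b, c)), with X binomial(b + c, 1/2), capped at 1. The plan states no alpha, so 0.05 is only a reference.

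- If EGD found all 21, then 4, 3 or 2 capsule misses give p = 2/16 = 0.125, 2/8 = 0.25 or 2/4 = 0.50. No conclusion changes.
- With 20 found by both and 5 by each test alone, p = 1.00. Upgrading four EGD-only findings and also downgrading four capsule-only findings gives b = 9 and c = 1, so p = 2 × 11/1024 = 0.021. Sensitivities are then 29/30 = 96.7% (EGD) and 21/30 = 70.0% (capsule).
- Over 10 or 20 concordant and 3, 5 or 8 discordant patients per side, p first falls below 0.05 at 3 to 5 regrades in each direction. Upgrading alone, up to six findings, never got there (lowest p = 0.146).

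**The case against.** The strongest reply is that the gap is hypothetical. No section says that a grader performs or cosigns the exams he or she grades. The capsule operator may be a nurse practitioner or a fellow, in which case an attending's documented link to the capsule exam is a cosignature only. Two attendings grade independently and their agreement is measured by kappa, so one interested grader does not alone fix the reference. If one grader did the EGD and the other cosigned the capsule report, their leanings could partly cancel. The study is a pilot with no power claim, and the illustrated shifts are smaller than its sampling error. Strict exclusion could also need four physicians per case (endoscopist, cosigner and two graders), and the documents do not say how many attendings the site has.

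Most of this stands, and it limits the point. It does not remove it: kappa measures disagreement without resolving it, and no provision prevents or records overlap.

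A reader might also infer that the two attendings are certainly the expert group and therefore the gold standard. The documents do not say so. They speak of study attendings and a reviewing group (6.7), a reader panel (10) and an expert group (synopsis, 4.2, 10.5) without linking them. Section 6.7 also mentions a kappa on three sets of observations, which does not obviously fit two graders, and 10.1 names EGD as the reference. The attendings' review is, however, the only grading process described. Even under 10.1 the D grade would still decide which findings count as positive.

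**Conclusion.** The plan permits self-grading of the subjective grade behind the primary endpoint, and none of its safeguards addresses this. Self-grading can bias the D1/D2 call on findings seen on one exam only, and with it the sensitivity of the capsule or of EGD. In the main illustration one or two regrades move capsule sensitivity from 81% to 85% or 89%, or down to 77% or 74% if the stake is in the EGD. This rests on the assumed counts and on the regrade setting the reference.

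Two stronger readings are not supported. One is that the graders do favour their own exam: overlap is possible but not shown, and the net direction is unknown. The other is that the comparison of the tests would be overturned: in the scenarios examined, that took 3 to 5 regrades in each direction at once. What is at risk is mainly the accuracy estimates, which are what a pilot delivers. As 6.7 specifies no record of who performed, signed and graded each case, the planned grading data would not show afterwards whether overlap occurred.

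**What to change.** In 6.7:

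1. State that the two attendings are the expert group, if that is intended, and reconcile 6.7 and 10.5 with the gold standard in 10.1.
2. Where existing staffing allows, assign each case to attendings who neither performed nor cosigned either exam.
3. Record the performer of each exam, the cosigner and the graders on the report sheet for every case, and flag any overlap.
4. Report the number of flagged cases and repeat the primary analysis without them.

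The cost is a scheduling constraint, three extra fields and one sensitivity analysis. That analysis will be imprecise if many of the 70 cases are flagged, but the count of flagged cases is informative in itself. No extra reader is required, and neither the sample size nor patient care changes.

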7 ETHICS

7.1 Regulatory Approval

The study will be conducted in compliance with the Declaration of Helsinki, ISO 14155:2011 standard, and 21 CFR part 812.

An IDE application was made to the FDA for the MCC tethered capsule. We received a nonsignificant risk letter from the FDA. Letter attached. The Navicam system is now FDA approved as of 5-22-2020

7.2 Investigational Review Board (IRB) Approval

The final version of the Clinical Study Protocol with the patient information and consent forms will be submitted by the Investigators to their IRBs prior to the commencement of the study.

7.3 Informed Consent

The Investigator must obtain from the patient or from his/her legal guardian a written informed consent for their inclusion in the study, after explaining its rationale and all details, including aims and objectives of the study, the risks and benefits and the extent of the patient's involvement. All patients must sign and date the informed consent.

The Investigator is responsible for ensuring that no patient is subject to any study-related examination or activity before the patient has given his/her written informed consent. After obtaining signature of the patient, duly signed informed consents will be kept and archived in the Investigator file, according to the requirements provided in 21 CFR 812.

7.4 Changes to Clinical Study Protocol or Related Procedures

Any changes to the clinical protocol or related procedures will be reported to the IRB before they are implemented.

7.5 Deviations from Clinical Study Protocol

Any deviation from the protocol shall be recorded and reported to the IRB and sponsor together with an explanation for the deviation.

Significant deviations defined as compromising or potentially compromising the safety of the patients, enrolment of non-eligible patients and any deviation which compromises significantly the outcome of the study, shall be subject to reporting to FDA and the IRB within the appropriate deadlines indicated by the regulations.

7.6 Patient Compensation

Product liability and No-Fault Clinical Trial Insurance covering the duration of the trial are in place, to enable compensation in the event of an injury to a participating patient.

Patients will be compensated for their inconvenience and travel expenses.

8 PATIENT BENEFIT AND RISKS

A risk management according to ISO 14971, has been conducted and is periodically reviewed. The risk management report is documented in NaviCam Capsule Endoscope System with NaviCam Stomach Capsule Risk Management Report (RM-NCES-ST-02). Risks have been proven minimized or eliminated through appropriate design control, confirmed by pre-clinical bench, laboratory, animal and clinical testing.

The NaviCam Stomach Capsule is MR unsafe. MRI exams should be avoided until capsule passage is confirmed.

Based on the available clinical data previously collected, the following anticipated adverse events may occur:

- Bloating
- Nausea
- Vomiting
- Headache
- Throat irritation
- Transient, two weeks retention of the capsule in the G.I. tract.

The main risk associated with the EGD procedure is perforation. Additionally, reaction to sedation may include:

- Difficulty breathing or an inability to breathe
- Low blood pressure
- Slow heartbeat
- Excessive sweating

Laryngeal spasm

Study Rationale

The safety and effectiveness of the NaviCam Stomach capsule has already been demonstrated via two clinical studies as well as in ongoing use in China and the EU. Basic usability and safety of the tether device was assessed by the company in healthy volunteers. The ability to visualize the esophagus utilizing the tether device may result in a simpler procedure that does not require sedation (when compared to EGD).

This study is designed to evaluate the safety and effectiveness of the NaviCam Stomach Capsule with Tether device for its intended use by comparing the obtained findings with those obtained via standard EGD.

9 ADVERSE EVENTS

9.1 Definition

Adverse Event (AE): Any untoward medical occurrence in a subject whether device related or not.

Serious Adverse Event (SAE): adverse event that

- a) led to death,
- b) led to serious deterioration in the health of the subject, that either resulted in:
 - 1) a life-threatening illness or injury, or
 - 2) a permanent impairment of a body structure or a body function, or
 - 3) in-patient or prolonged hospitalization, or
 - 4) medical or surgical intervention to prevent life-threatening illness or injury or permanent impairment to a body structure or a body function,
- c) led to fetal distress, fetal death or a congenital abnormality or birth defect

NOTE Planned hospitalization for a pre-existing condition, or a procedure required by the CIP, without serious deterioration in health, is not considered a serious adverse event.

Serious Adverse Device Effect (SADE): Adverse Event caused by or involving the device that has resulted in any of the consequences characteristics of a Serious Adverse Event. A SADE may occur at any time after exposure to the study device.

Unanticipated Adverse Device Effect (UADE): Any serious adverse effect on health or safety or any life-threatening problem or death caused by, or associated with, a device, if that effect, problem, or death was not previously identified in nature, severity, or degree of incidence in the investigational

plan or application (including a supplementary plan or application), or any other unanticipated serious problem associated with a device that relates to the rights, safety, or welfare of subjects.

All adverse events will be graded for severity as follows:

Mild: Sign or symptom, usually transient, requiring no special treatment and generally not interfering with usual activities.

Moderate: Sign or symptom, which may be ameliorated by simple therapeutic measures; yet, may interfere with usual activity.

Severe: Sign or symptom that are intense or debilitating and that interfere with usual activities. Recovery is usually aided by therapeutic measures.

The relationship of the adverse event to the investigational device use is defined as follows:

Probably related: Follows a reasonable temporal sequence from study device delivery/retrieval and cannot be reasonably explained by known characteristics of the subject's clinical data.

Possibly related: Follows a reasonable temporal sequence from study device delivery/retrieval but could have been produced by the subject's clinical state regardless of the study device.

Not related: No relationship to study device activation is perceived.

Occurrence of death, whether or not it is assessed as related to the device, must be well-documented. The information should include the date expired, cause of death, what attempts were made to treat the condition, the performance and functioning of the device prior to the event and causal relationship to the device. If device or procedure relation cannot be ruled out, an autopsy should be encouraged.

9.2 Handling and Reporting of Adverse Events and Device Deficiencies

Patients will be carefully monitored during the study for possible adverse events. Any adverse events observed will be fully investigated by the Investigator. Appropriate treatment, if needed of the patient will be initiated.

The Investigator will attempt to assess the involvement of the investigational procedure in the adverse event. All observations and clinical findings, including the nature, severity, will be documented on the CRF (Adverse Events).

The Investigator will report all serious adverse events to the IRB and sponsor by telephone or e-mail within twenty-four hours.

ANX Robotica will report the results of an evaluation of an unanticipated adverse device effect to FDA and the reviewing IRBs and investigators within 10 working days after the sponsor first receives notice of the adverse effect.

10 DATA MANAGEMENT AND STATISTICAL CONSIDERATIONS

Study will be performed according to the protocol. The investigator will appoint a person that will be responsible to complete the Case Report Forms using the REDCap system, a secure data collection system. Source documentation will be either paper documents or the electronic medical record.

All relevant documents such as MCC images/videos, EGD images/videos, etc. will be uploaded to the EDC. Patient identification will be redacted from all data. Patients will be identified by their patient ID. The list of patient IDs will be kept in the site and will not be available for the sponsor.

The EDC system will provide streamlined communication between the study monitors, data managers and study coordinators. The system will allow the generation of queries which will need to be responded to and resolved by the relevant personnel.

De-identified color images will be used by the reader panel to compare MCC-T and endoscopy images.

